12.1.3. Additional Treatment Discontinuations

The following events are considered sufficient reasons for discontinuing a subject from the investigational product and/or from the study:

- Adverse event(s)
- Withdrawal by subject
- Death
- Lost to follow-up
- Protocol violation
- Pregnancy

- Recovery
- Non-compliance with IP
- Study terminated by sponsor
- Physician decision
- Screen failure
- Technical problems
- Disease relapse
- Failure to meet randomization criteria
- Site terminated by sponsor
- Completed
- Other (to be specified in the eCRF)

The reason for discontinuation of treatment should be recorded in the eCRF and in the source documents.

The decision to discontinue a subject from treatment remains the responsibility of the treating physician, which will not be delayed or refused by the Sponsor. However, prior to discontinuing a subject, the Investigator may contact the Medical Monitor and forward appropriate supporting documents for review and discussion.

Subjects who discontinue will have laboratory assessments performed as specified in the Early Termination Column in the Table of Events (Table 1).

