Quantitative Sudomotor Axon Reflex Testing (QSART)	Х	-	-	-	-	-	-	-	Х	-	-	Х	-	Х			
Skin biopsies	Х	-	-	-	-	Х	-	-	Х	-	-	-	-	-			
Histology of Immune Cells (mast cell)	Х	-	-	-	-	Х	-	-	Х	-	-	-	-	-			
Norfolk Quality of Life Assessment (Norfolk-QOL-DN)	Х	-	-	-	-	Х	-	-	Х	-	-	Х	-	Х			
Patient Global Impression of Change in Neuropathy (PGICN)	X	Х	Х	X	X	-	-	-	Х	-	-	X	-	X			

	Screening Period	Treatment Period				Follow-up Period								
	V1	V2	V3	V4	V5	V6	V7	V8	V9	V10	V11	V12	V13	
	Day -28 to Day 0	Day 1 (±3 days)	Day 15 (±3 days)	Day 29 (±3 days)	Day 57 (±3 days)	Day 93 (±7 days)	Day 120 (±3 days)	Day 155 (±3 days)	Day 186 (±7 days)	Day 246 (±7 days)	Day 306 (±7 days)	Day 365 (±7 days)	Day 425 (±7 days)	Early Termin- ation
Event		Week 1	Week 2	Month 1	Month 2	Month 3	Month 4	Month 5	Month 6	Month 8	Month 10	Month 12	Month 14	
Vascular reactivity measurements- (including Laser Doppler Iontophoresis and Nerve Axon Reflex measurements)	Х	-	-	-	-	Х	-	-	Х	-	-	Х	-	-
Administration of IP	-	Х	-	Х	Х	-	-	-	-	-	-	-	-	-
IP administration monitoring (including visual inspection of injection areas, vital signs, and collection of blood for coagulation tests and tryptase/histamine evaluation before and after IP administration)	-	Х	-	х	х	-	-	-	-	-	-	-	-	-
Assess and record adverse events ^d	Х	Х	Х	Х	Х	Х	Х	Х	Х	Х	Х	Х	X	Х

Table 1:Table of Events (Continued)

Abbreviations: IP=Investigational Product, PBMC=peripheral blood mononuclear cell, RBC=red blood cell, SAE=serious adverse event.

^a Physical exams during the Screening Period and Early Termination will be full physical examinations. At all other assessments, physical examinations should only be directed to evaluate reported adverse events. Assessments for vital signs can be performed within15 minutes for the 1 and 2 hour post dose assessments.

^b Biomarkers assessed at Screening, Visit 2 Day 1 and Visit 4 Day 29, and Visit 5 Day 57 prior to injection of IP. Biomarkers will also be assessed on Day 93 when there is no IP injection. Biomarker samples will include blood immune biomarkers and RBC-lysed PBMC sample for the chip cytometry assay. The chip cytometry assay will only be performed at selected sites.

^c Serum pregnancy testing at Screening and urine pregnancy testing at all other visits of females of childbearing potential. At Visit 2 a urine pregnancy needs to be performed if a serum pregnancy test was not done within 0-72 hours predose. Prior to treatment on Study Days 1, 29, and 57.

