8.2.1. Discontinuation

The reason for discontinuation should be recorded in the eCRF and in the source documents. The decision to discontinue a subject remains the responsibility of the treating physician, which will not be delayed or refused by the sponsor. However, prior to discontinuing a subject, the investigator may contact the Medical Monitor and forward appropriate supporting documents for review and discussion. Of note, the investigator is not required to contact a medical monitor to discuss discontinuation or unblinding as the investigator has the ability to discontinue or rapidly unblind subjects.

Subjects who discontinue will have the procedures performed as listed in the Early Termination column as per the Table of Events (Table 1).

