12.1.2. Mandatory Treatment Discontinuations

Should subjects experience any of the following events, they may not receive additional doses of PDA-002. They should stay on study however, and all scheduled evaluations are to be performed.

- A Grade 3 or higher allergic reaction within 24 hours of PDA-002 administration.
- An episode of symptomatic arterial vasospasm within 24 hours of PDA-002 administration. Examples include acute coronary ischemia and retinal artery spasm.
- An episode of new venous thrombosis within 3 days of PDA-002 administration.

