12.2. Study Discontinuation

The following events are considered sufficient reasons for discontinuing a subject from the study:

- Screen failure
- Adverse event(s)
- Withdrawal by subject
- Death
- Lost to follow-up
- Other (to be specified in the eCRF)

The reason for study discontinuation should be recorded in the eCRF and in the source documents.

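### Sections 12.1.3 and 12.2 disagree on what ends study participation, and the Early Termination route has no biopsy, so Month 6 ENFD can be lost for response-related reasons

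*Combined protocol and SAP*

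**What the plan says.** Four places in the protocol bear on who leaves and what is then measured.

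- **Section 12.1.3** introduces its list with "The following events are considered sufficient reasons for discontinuing a subject from the investigational product and/or from the study". The list has 17 entries. One is "Disease relapse", another is *Recovery*.
- **Section 12.2** introduces a second list with "The following events are considered sufficient reasons for discontinuing a subject from the study". It has six entries: screen failure, adverse event, withdrawal by subject, death, loss to follow-up, and an open other category.
- **Section 12.1.2** says of subjects who must stop IP: "They should stay on study however, and all scheduled evaluations are to be performed". It applies to three events: a Grade 3 or higher allergic reaction, symptomatic arterial vasospasm and new venous thrombosis, each within a stated time of dosing.
- **Section 8.2.1** says: "Subjects who discontinue will have the procedures performed as listed in the Early Termination column as per the Table of Events (Table 1". Section 12.1.3 ends with a similar sentence that speaks only of laboratory assessments in the same column.

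The primary endpoint (Section 3.1) is change from baseline in ENFD at 6 months, measured on skin biopsy. In Table 1 the row "Skin biopsies" is marked at Visits 1, 6 and 9 and shows a dash under Early Termination.

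**The concern.** A site reading Section 12 cannot tell which list decides whether a subject leaves the study or only stops IP. That matters because two reasons found only in 12.1.3 describe the course of the disease under study. If either is used to end participation before Visit 9, the missing Month 6 ENFD is related to how the subject responded.

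The trial is small (8 per arm), and Section 10.3 says that it is meant to estimate the treatment effect so that the next study can be sized. Response-related loss of the primary measurement would distort that estimate, and no analysis can recover a biopsy that was not taken. The protocol gives no dropout allowance and no rule for missing Month 6 ENFD, and leaves analysis detail to a separate SAP.

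**Working it through.** **1. Compare the lists.** All six entries in 12.2 also appear in 12.1.3, so 17 − 6 = 11 appear only in 12.1.3:

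| Type | In 12.1.3, not named in 12.2 |
|---|---|
| Disease course | recovery; disease relapse |
| Conduct | protocol violation; non-compliance with IP; failure to meet randomization criteria; technical problems |
| Clinical | pregnancy; physician decision |
| Administrative | study terminated by sponsor; site terminated by sponsor; completed |

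**2. Trace the biopsy.** A subject leaves under 12.1.3, is sent to the Early Termination column, and has no biopsy there. The last scheduled biopsy before Visit 9 is at Visit 6 (Day 93), and ENFD at that visit is exploratory. Exit before Visit 9 (Day 186) means no primary endpoint value. The subject can still be in the mITT population, which needs only some IP and one later efficacy assessment (Section 10.2).

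**3. Timing.** The last dose is on Day 57, and 186 − 57 = 129 days remain to Visit 9. In that window there is no IP left to stop, so only the study-exit half of 12.1.3 can have any effect.

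**4. Reproduce the plan's power.** Inputs from Section 10.3: effect 3.07 − 1.56 = 1.51 fibers/mm, no change on placebo, SD 1.5, 16 active v 8 placebo, two-sided 0.05.

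- Active v placebo: noncentrality = 1.51 / (1.5 × √(1/16 + 1/8)) = 2.32 on 22 df. Noncentral t power is 60.4%; the plan states 60%.
- Change within the 16 active subjects, one-sample t: 96.4%; the plan states 96%.

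**5. Illustrate selective loss.** The documents give neither the number who would leave nor the correlation (rho) between clinical improvement and ENFD change, so both are assumed. Suppose 2 of the 16 active subjects leave and no placebo subject does.

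In the extreme case where the two largest ENFD changes are lost (rho = 1), simulation gives a mean for the other 14 of about 1.18, a shift of 1.51 − 1.18 = 0.33. Under a normal model the shift is proportional to rho, so at rho 0.5 it is 0.5 × 0.33 ≈ 0.16, and 1.51 − 0.16 = 1.35. Power comes from simulation with a pooled t-test.

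| Two active subjects lost | Expected difference | Power |
|---|---|---|
| None lost | 1.51 | 60% |
| At random | 1.51 | 58% |
| Most improved, rho 0.3 | 1.41 | 53% |
| Most improved, rho 0.5 | 1.35 | 51% |
| Most improved, rho 0.7 | 1.28 | 49% |

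About two points of the power drop are ordinary loss of sample; the rest is bias. If the two *least* improved leave instead, the shift has the opposite sign: at rho 0.5, 1.51 + 0.16 = 1.67.

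**The case against.** The best defence is that 12.1.3 reproduces a generic disposition menu. It includes *Completed* and *Screen failure*, which cannot sensibly be reasons to remove a treated subject. It sits under a heading on treatment discontinuation, and the text after the list speaks of stopping treatment. Both lists give sufficient reasons, so both are permissive, and the open category in 12.2 could absorb anything in 12.1.3. No site could follow one section and breach the other.

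Much of this stands. It makes the fault one of drafting rather than of two incompatible rules. It does not remove the fault: the lead-in to 12.1.3 expressly reaches study exit, the two disease-course reasons are undefined, and a residual category does not tell a site when follow-up should end.

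Three stronger readings are tempting, and the documents support none of them:

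- **That the plan removes responders.** Nothing directs a site to release improved subjects. The wording allows it and does not require it.
- **That 12.1.2 shows a general intention to keep subjects on study after IP stops.** Its sentence covers three safety events only. Elsewhere, subjects who discontinue are sent to Early Termination procedures.
- **That non-compliance or protocol violation excludes subjects from the analysis.** The mITT definition does not do so. What may be lost is the Month 6 measurement.

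**Conclusion.** The point holds as an ambiguity with a consequence for the primary endpoint. Sections 12.1.2, 12.1.3, 12.2 and 8.2.1 do not together say which reasons end participation or whether a subject who stops IP still has the Visit 9 biopsy. A subject who leaves before that visit has no Month 6 ENFD, and two permitted reasons are related to response.

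The size cannot be stated from the documents. The fall from 1.51 to about 1.35 and from 60% to about 51% power rests on three assumptions: two exits, all in the active arms and all among the most improved, with rho 0.5. A reader might infer that the bias runs against PDA-002. That does not follow: exits for relapse would push the estimate up, exits on placebo would matter too, and the net direction is unknown. The case for changing the text is that the plan permits such loss and that the repair costs little.

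**What to change.** Reconcile Sections 12.1.2, 12.1.3, 12.2 and 8.2.1:

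1. Separate the reasons that end IP only from those that end study participation. Keep withdrawal by subject, death, loss to follow-up, and sponsor or site termination (Section 14.8) as study exits. The sponsor should assign each remaining entry explicitly.
2. State that recovery, disease relapse, non-compliance with IP and protocol violation do not by themselves end study follow-up.
3. State that subjects who stop IP but have not left the study keep their scheduled Table 1 visits, including the Visit 9 biopsy. Reserve Early Termination procedures for those leaving the study, and make the closing sentences of 8.2.1 and 12.1.3 agree. Editing the lists alone would leave that routing in place.

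Nothing here changes when IP is stopped. The cost is rewording in four sections and a matching eCRF disposition page, with no visit or procedure beyond Table 1. The small downside is continued follow-up of a few subjects who would otherwise be released.

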Efficacy will also be assessed in an exploratory manner by evaluating changes from baseline in the following:

- ENFD at 3 months
- Microvascular oxygenation of the lower limbs by Hyperspectral Imaging (HSI)

- Vascular reactivity by Laser Doppler Iontophoresis and Nerve Axon Reflex measurements.
- The 6-item Neuropathy Total Symptom Score (NTSS-6) assessment
- The Neurological Impairment Score of the Lower Limb (NIS-LL)
- The Utah Early Neuropathy Scale (UENS)

Additional efficacy signals indicating changes in motor and sensory nerve conduction and autonomic function as evaluated by:

- Nerve conduction studies
- Quantitative Sudomotor Axon Reflex Testing (QSART). QSART is a measurement of autonomic involvement by evaluating postganglionic sudomotor function deficits in the foot, distal leg, and distal thigh.

Changes in health-related quality of life (QOL) will be assessed by the Norfolk QOL-DN.

Various experimental biomarker analyses will be performed to assess changes in the vascular and immune profile. Samples for biomarker analyses will include blood and epidermal tissue. In addition, an assessment of the systemic vs. local efficacy of PDA-002 will be evaluated.

Overview of Safety Assessments

Safety and tolerability will be assessed by the type, frequency, and severity of adverse events (AEs). As such, the following safety assessments will be performed as outlined in the Table of Events (Table 1).

- Assessment of adverse events and serious adverse events (SAEs)
- Physical examinations including complete neurological examinations and vital signs
- Clinical laboratory tests including chemistry, hematology, urinalysis, evaluation; urine pregnancy testing if applicable
- Twelve-lead electrocardiogram (ECGs)
- Retinal assessments
- Concomitant medications and procedures
- Immunological assessments
 - Anti-human leukocyte antigen (HLA) antibodies

Sample Size and Power Considerations

The sample size of 24 subjects total, 8 per treatment arm, was selected in order to provide preliminary efficacy and safety information in a randomized, double-blind fashion. The study is designed to provide an estimation of the treatment effect of active therapy and placebo to plan a sample size for the next study.

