5. TABLE OF EVENTS

Table 1:Table of Events

	Screening Period		Treatment Period								Follow-up Period					
	V1	V2	V3	V4	V5	V6	V7	V8	V9	V10	V11	V12	V13			
	Day -28 to Day 0	Day 1 (±3 days)	Day 15 (±3 days)	Day 29 (±3 days)	Day 57 (±3 days)	Day 93 (±7 days)	Day 120 (±3 days)	Day 155 (±3 days)	Day 186 (±7 days)	Day 246 (±7 days)	Day 306 (±7 days)	Day 365 (±7 days)	Day 425 (±7 days)	Early Termin- ation		
Event		Week 1	Week 2	Month 1	Month 2	Month 3	Month 4	Month 5	Month 6	Month 8	Month 10	Month 12	Month 14			
Informed consent	Х	-	-	-	-	-	-	-	-	-	-	-	-	-		
Inclusion/exclusion criteria	Х	-	-	-	-	-	-	-	-	-	-	-	-	-		
Demography/medical and surgical history including duration of diabetes and diabetic peripheral neuropathy	Х	-	-	-	-	-	-	-	-	-	-	-	-	-		
Prior/concomitant medication and procedures	Х	X	Х	Х	Х	Х	Х	Х	Х	Х	Х	Х	Х	Х		
Physical examination including vital signs (height [at Visit 1 only], weight, body temperature, blood pressure, respiration, and pulse ^a	Х	x	-	х	х	X	Х	х	X	X	х	х	Х	Х		
12-Lead electrocardiogram (ECG) ^f	Х	-	-	-	-	-	-	-	-	-	-	-	-	-		
Clinical laboratory testing (serum biochemistry, hematology, coagulation tests urinalysis). Estimated glomerular (eGFR) filtration rate will be calculated (Screening).	Х	х	-	х	Х	-	-	-	х	-	-	-	Х	Х		
Anti-HLA antibodies	Х	Xe	-	Xe	Xe	Х	-	-	-	-	-	-	-	-		
HbA1c testing	Х	-	-	-	-	Х	-	-	Х	-	-	Х	-	Х		
Obtain blood for exploratory biomarker evaluation prior to administration of IP ^b	X	X	-	X	X	X	-	-	X	-	-	-	-	X		

I able 1: I able of Events (Continue)

	Screening Period	Treatment Period									Follow-up Period						
	V1	V2	V3	V4	V5	V6	V 7	V8	V9	V10	V11	V12	V13				
	Day -28 to Day 0	Day 1 (±3 days) Week	Day 15 (±3 days) Week	Day 29 (±3 days) Month	Day 57 (±3 days) Month	Day 93 (±7 days) Month	Day 120 (±3 days) Month	Day 155 (±3 days) Month	Day 186 (±7 days) Month	Day 246 (±7 days) Month	Day 306 (±7 days) Month	Day 365 (±7 days) Month	Day 425 (±7 days) Month	Early Termin- ation			
Event		1	2	1	2	3	4	5	6	8	10	12	14				
Pregnancy test ^c	Х	Х	-	Х	Х	-	-	-	-	-	-	-	-	Х			
Retinal examination	Х	-	-	-	-	-	-	-	Х	-	-	Х	-	Х			
6 Item Neuropathy Total Symptom Score (NTSS-6)	Х	-	-	Х	-	Х	-	-	Х	-	-	Х	-	Х			
Utah Early Neuropathy Scale (UENS)	Х	-	-	Х	-	Х	-	-	Х	-	-	Х	-	Х			
Neuropathy Impairment Score of the Lower Limb (NIS-LL)	Х	-	-	Х	-	Х	-	-	Х	-	-	Х	-	Х			
Electrophysiologic nerve conduction studies	Х	-	-	-	-	-	-	-	Х	-	-	Х	-	Х			
Hyperspectral imaging	Х	-	-	Х	-	Х	-	-	Х	-	-	Х	-	Х			

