^d Adverse events will be followed for 28 days after the last dose of IP. SAEs will be followed until the last study visit.

^e Prior to injection on Days 1, 29 and 57.

^f If performed within 28 days of signing the informed consent it does not need to be repeated.

6. **PROCEDURES**

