8. DESCRIPTION OF STUDY TREATMENTS

8.1. Description of Investigational Product

PDA-002 is characterized as a cellular angiogenic and immune modulating agent with therapeutic potential. The product contains a mesenchymal-like cell population derived from normal, full-term human placental tissue. The cells are culture-expanded as a plastic-adherent, undifferentiated in vitro cell population that expresses the nominal phenotype CD34-, CD10+, CD105+, and CD200+. The cells constitutively express moderate levels of HLA Class I and undetectable levels of HLA Class II.

These cells demonstrate a range of potential biological activities which include the ability to (1) induce endothelial cell survival, migration and tube formation, showing angiogenic and cytoprotective potential, and (2) modulate T-cell repertoire and affect the M1/M2 balance of macrophages demonstrating an immune modulatory effect. Based on these properties, the proposed study will evaluate the safety of PDA-002 in subjects with DPN.

PDA-002 or placebo (vehicle control) units will be shipped to the study sites as cryopreserved units and will be thawed and filled into syringes prior to IM injection. A PDA-002 unit are supplied at 2 dosage strengths and contains approximately 3 or 30 million cells in 4.5 mL of a 5.75% dextran 40/10% human serum albumin (HSA) solution containing 2.5% DMSO for cryopreservation. The solution also contains Plasma-Lyte and saline to maintain the cells' osmotic environment. Placebo (vehicle control) units contain the above-mentioned components, without any cells. The product is intended for allogeneic use.

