10.2. Study Population Definitions

The following analysis populations are planned for this study:

Screening Population (Screen): The Screening Population includes all subjects who provide informed consent and screen for eligibility during the Screening Period (Day -28 to Day -1).

Safety Population (Safety): The Safety Population includes all subjects who receive any amount of IP.

Modified Intent To Treat (mITT): The mITT population includes all subjects who receive any amount of IP and subsequently provide at least one efficacy assessment.

Other study populations or subgroup populations may be identified during the course of this study. Any additional study populations or subgroups will be clearly identified either in the SAP or, if after database lock, then as post-hoc study populations in the clinical study report.

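### Table 1 has no anti-HLA draw at Early Termination, so a subject who leaves the study between dose 1 and the Day 29 draw has no scheduled post-dose result: a minor gap, cheap to narrow.

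*Combined protocol and SAP*

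**What the plan says.** The Protocol Summary, under Overview of Safety Assessments, lists "Anti-human leukocyte antigen (HLA) antibodies" as an immunological assessment. Section 8.1 says of the product: "The product is intended for allogeneic use". It is given three times, on Days 1, 29 and 57.

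Section 6.1 sets the anti-HLA schedule only by pointing to Table 1. There the row "Anti-HLA antibodies" is marked at Screening, Day 1, Day 29, Day 57 and Day 93. Footnote e times the three dosing-day samples: "Prior to injection on Days 1, 29 and 57". Day 15, every visit after Day 93, and Early Termination carry a dash.

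Two sections send subjects who stop to the Early Termination column. Section 8.2.1: "Subjects who discontinue will have the procedures performed as listed in the Early Termination column as per the Table of Events (Table 1"). Section 12.1.3: "Subjects who discontinue will have laboratory assessments performed as specified in the Early Termination Column in the Table of Events (Table 1"). That column is marked for clinical laboratory tests, for HbA1c, and for the row "Obtain blood for exploratory biomarker evaluation prior to administration of IP".

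Section 10.2 defines the safety set: "The Safety Population includes all subjects who receive any amount of IP".

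**The concern.** The plan takes exploratory blood from a subject who leaves early but does not schedule the antibody test that it lists under safety. For a repeat-dosed allogeneic product, whether a subject became sensitised is a natural safety question. Someone who leaves soon after the first dose remains in the Safety Population with nothing scheduled to answer it. A sample that was not taken cannot be recovered by any later analysis rule, so the schedule is the place to deal with it.

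What is at stake is the completeness of one descriptive safety measure in arms of 8.

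**Working it through.** No figure in the plan needs reproducing here. The check is a reading of Table 1 and some date arithmetic.

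**Table 1, cell by cell.** There are 14 columns: Visits 1 to 13 and Early Termination. Each row below has 14 cells, so the last cell is Early Termination and the anti-HLA dash is not a product of text extraction.

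| Row | Marked at | Early Termination |
|---|---|---|
| Anti-HLA | V1, V2, V4, V5, V6 | dash |
| Clinical laboratory | V1, V2, V4, V5, V9, V13 | marked |
| HbA1c | V1, V6, V9, V12 | marked |
| Exploratory biomarker blood | V1, V2, V4, V5, V6, V9 | marked |

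**Which draws are post-dose.** By footnote e, the Day 1 sample precedes dose 1, so the first post-dose draw is the pre-injection sample on Day 29. The Day 57 sample is the first after dose 2, and the Day 93 sample is the first after dose 3.

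**Scheduled post-dose results for a subject who leaves the study:**
- after dose 1, before the Day 29 draw: 0
- after dose 2, before the Day 57 draw: 1, with none after dose 2
- after dose 3, before the Day 93 draw: 2, with none after dose 3
- after the Day 93 draw: no scheduled draw is missed

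**Length of each window**, from the nominal days and the visit windows (±3 days for the dosing visits, ±7 for Day 93):
- Dose 1 to Day 29: 29 − 1 = 28 days; range (29 − 3) − (1 + 3) = 22 to (29 + 3) − (1 − 3) = 34.
- Dose 2 to Day 57: 57 − 29 = 28 days; range (57 − 3) − (29 + 3) = 22 to (57 + 3) − (29 − 3) = 34.
- Dose 3 to Day 93: 93 − 57 = 36 days; range (93 − 7) − (57 + 3) = 26 to (93 + 7) − (57 − 3) = 46.

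**Scale.** One unmeasured subject is 1/8 = 12.5% of an arm, or 1/16 = 6.25% of the pooled active subjects. As an illustration only, assume that 0, 1 or 2 of 8 are unmeasured, all are negative at baseline, and no new antibody appears among those measured. The share of dosed subjects with a new antibody could then be 0%, 0% to 12.5%, or 0% to 25%. The exact two-sided 95% upper limit for 0 of n is 1 − 0.025^(1/n): 36.9% for n = 8, 41.0% for n = 7, 45.9% for n = 6. The limit is already wide with nobody missing.

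**Effect of the added mark.** A dose-1 leaver who attends Early Termination has 1 post-dose result instead of 0. How informative it is depends on timing. The shortest scheduled dose-to-draw interval is 22 days, so a sample taken 1 to 21 days after dose 1, which is 21/28 = 75% of that window, comes earlier than any scheduled draw would.

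**The case against.** The strongest reply concerns consequence, since the reading of Table 1 is not in doubt. The secondary endpoint in section 3.2 is measured by adverse events. Neither section 6.5 nor section 10.7 names anti-HLA, and the protocol states no seroconversion rate over the Safety Population. Acute reactions are watched at each dose by tryptase, histamine, vital signs and inspection of the injection sites. Section 10.7 allows laboratory tests to be repeated when clinically indicated. An added draw in the dose-1 window would often be too soon for a negative to mean much. All of this stands and keeps the point minor. It does not remove the gap: the repeat provision is discretionary, and the other monitoring does not measure antibody.

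A reader might infer more than the documents support:
- **That missing results depend on tolerability.** Adverse events are a listed reason for leaving (section 12.2), but nothing links lesser reactions to anti-HLA status. Subjects stopped under section 12.1.2 for a Grade 3 or higher allergic reaction, arterial vasospasm or venous thrombosis stay on study and keep their scheduled draws.
- **That the dose-1 window is a 30% risk.** 28/(93 − 1) = 30.4% is a share of days. Over the whole schedule it is 28/(425 − 1) = 6.6%. Neither is a probability of leaving.
- **That 22 days separates readable from unreadable negatives.** That number comes from visit windows; the documents give it no immunological meaning.
- **That everyone who stops the product is unsampled.** Section 12.1.3 covers stopping the product, the study, or both. Those who stop only the product may still attend scheduled visits.

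**Conclusion.** The gap is real and narrow. It concerns subjects who leave the study after a dose and before the next anti-HLA draw. After dose 1 they have no scheduled post-dose result; after dose 2 or 3 they have none following the last dose. Each is 12.5% of an arm of 8. How many there will be is unknown, because the documents give no dropout rate; with no antibody rate either, the size and direction of any bias cannot be stated and none is demonstrated. The primary ENFD analysis, its power and its error rate, and the adverse-event secondary endpoint are untouched.

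This is a minor, cheap improvement. The gain lies mainly in positive results, in draws taken later in a window, and in leavers after dose 2 or 3. The conclusion assumes that leavers attend the Early Termination visit and that no document outside those reviewed, such as the Laboratory Manual, already adds the sample.

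**What to change.** In Table 1, mark anti-HLA antibodies at Early Termination, with a footnote limiting it to subjects in any arm who leave the study after any dose and before the Day 93 draw. In the listing, show the days since the last dose beside each anti-HLA result, so that an early negative is not taken as absence of sensitisation. Injection times are already recorded under section 6.2, so this needs only the draw date. No fixed cutoff in days is needed.

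The cost is one mark, one footnote, one derived column and at most one extra assay per such leaver, sampled at a visit where blood is already drawn. No visit is added. It will not recover subjects who die, are lost to follow-up or decline the visit, and a negative drawn within about the first three of the four weeks after dose 1 may be uninformative.
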